**Table 30. Univariate Cox regression PFS**

Variables	Categories	HR	p-value	95% CI HR		N
				Inferior	Superior	
ENO1	Yes					
	No					
	Total					
VEGFR2	Yes					
	No					
	Total					
VEGFR3	Yes					
	No					
	Total					
IL8	Yes					
	No					
	Total					
CYP3A4	Yes					
	No					
	Total					
ABCB1	Yes					
	No					
	Total					
POR	Yes					
	No					
	Total					
HIF1- $\alpha$	Yes					
	No					
	Total					
CYP2W1	Yes					
	No					
	Total					
c-Myc	Yes					
	No					
	Total					

In the total analysis population, in the multivariate model, those variables that were found statistically significant ( $p < 0,1$ ), will be entered as factors in the multivariate model for PFS.

**Table 31. Multivariate logistic regression PFS**

Variables	Categories	HR	p-value	95% CI HR		N
				Inferior	Superior	
ENO1	Yes					
	No					
	Total					
VEGFR2	Yes					
	No					
	Total					
VEGFR3	Yes					
	No					
	Total					
IL8	Yes					
	No					
	Total					
CYP3A4	Yes					
	No					
	Total					
ABCB1	Yes					
	No					
	Total					
POR	Yes					
	No					
	Total					
HIF1- $\alpha$	Yes					
	No					
	Total					
CYP2W1	Yes					
	No					
	Total					
c-Myc	Yes					
	No					
	Total					

### 2.7.2.8 Association between OS and Biomarkers

In the total analysis population, the association between the marker expression profiles analysed in plasma and OS will be assessed using the Cox regression models (univariate and multivariate).

**Table 32. Univariate Cox regression OS**

Variables	Categories	HR	p-value	95% CI HR		N
				Inferior	Superior	
ENO1	Yes					
	No					
	Total					
VEGFR2	Yes					
	No					
	Total					
VEGFR3	Yes					
	No					
	Total					
IL8	Yes					
	No					
	Total					
CYP3A4	Yes					
	No					
	Total					
ABCB1	Yes					
	No					
	Total					
POR	Yes					
	No					
	Total					
HIF1- $\alpha$	Yes					
	No					
	Total					
CYP2W1	Yes					
	No					
	Total					
c-Myc	Yes					
	No					
	Total					

In the total analysis population, in the multivariate model, those variables that were found statistically significant ( $p < 0,1$ ), will be entered as factors in the multivariate model for OS.

**Table 33. Multivariate logistic regression OS**

[figure not shown]
Variables	Categories	HR	p-value	95% CI HR		N
				Inferior	Superior	
ENO1	Yes					
	No					
	Total					
VEGFR2	Yes					
	No					
	Total					
VEGFR3	Yes					
	No					
	Total					
IL8	Yes					
	No					
	Total					
CYP3A4	Yes					
	No					
	Total					
ABCB1	Yes					
	No					
	Total					
POR	Yes					
	No					
	Total					
HIF1- $\alpha$	Yes					
	No					
	Total					
CYP2W1	Yes					
	No					
	Total					
c-Myc	Yes					
	No					
	Total					

**2.7.2.9 ROC curves: Area Under Curve, ORR vs. Biomarkers**

The predictive value (of genetic biomarkers, in plasma and tumour tissue) of each model previously obtained assessing the factors (marker expression profiles analysed in plasma) of treatment response (yes/no). The accuracy will be measured by the area under the ROC curve. An area of 1 represents a perfect test and an area of 0,5 represent a worthless test. A rough guide for classifying the accuracy of a diagnostic test is the traditional academic point system:

- 0,90-1 = excellent (A)
- 0,80-0,90 = good (B)
- 0,70-0,80 = fair (C)
- 0,60-0,70 = poor (D)
- 0,50-0,60 = fail (F)

Figure 7 ROC curve: ORR vs. Biomarker model 1

## 2.8. SAFETY ANALYSIS

Adverse events and serious adverse events, laboratory test results, physical examination findings and vital signs, and their changes from baseline will be summarized using descriptive statistics. Abnormal values will be flagged.

The total analysis population will be used for the safety analysis.

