With these encouraging results (better than doxorubicin as monotherapy), a randomised phase III study (TH-CR-406) was conducted to assess the administration of TH-302 at doses of 300 mg/m² weekly in combination with a routine doxorubicin regimen (NCT01440088).

From the work which identified an increase in the hypoxic fraction with sunitinib at 40 mg/m² in 786-0 renal cell carcinoma murine models, and the activity of TH-302 in hypoxic tissues, its research in humans began with the conduct of a phase I dose-escalation clinical trial (32). This study combined TH-302 with sunitinib in patients with renal cell carcinoma, gastrointestinal stromal tumour (GIST) and pancreatic neuroendocrine tumour (pNET) in first line or successive. GIST and pNET were only included in the dose escalation phase. The recommended dose of sunitinib was 50 mg daily for 28 days in 42-day cycles (6 weeks) in combination with TH-302 at a dose 340 mg/m² by intravenous infusion on days 8, 15 and 22 of each 42-day cycle (6 weeks). There was no DLT at a dose of 240 mg/m² (N = 4), 1 DLT was observed at 340 mg/m² (N = 6), which was a grade 2 stomatitis. Grade 3/4 neutropenia and thrombopenia was observed in 3 and 5 patients, respectively. The most common adverse events associated with TH-302 were nausea and mucositis. Preliminary data showed synergistic activity of sunitinib plus TH-302 in patients with renal cell carcinoma progressing to sunitinib (figure 3).

Figure 3. Change in tumour volume with the combination therapy sunitinib+TH-302.

A phase II trial to assess the activity and safety of TH-302 in combination with sunitinib in patients

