ANNEX 1. SCHEDULE OF ASSESSMENTS

	Screening (28 days)	Cycles				End of treatment (at 4 weeks +/- 1) after the end of treatment	Follow-up until progression (every 8 weeks until progression)	Post- progression follow-up
		Day 1 (D1)	Week 2 (D8)	Week 3 (D15)	Week 4 (D22)			
Informed consent ¹	X							
Inclusion/exclusion criteria	X							
Medical record and demographic data ²	X							
Physical examination (weight, height and vital signs)	X	X	X	X	X	X	X	
Signs/symptoms		X	X	X	X	X	X	
ECOG performance status ^(Annex 3)	X	X	X	X	X	X	X	
Haematology and haemostasis ⁴	X	X	X	X	X	X	X	
Full clinical chemistry ⁵	X	X	X	X	X	X	X	
NET markers ⁶	X	Every 8 weeks from D1C1 until progression and end of treatment visit.						
Pregnancy test ⁷	X ≤ 7 days)							
12-lead ECG ⁸	X		X ⁸		X ⁸			
Urinalysis	X					X		
Echocardiogram/MUGA ⁹	X					X		
Recording of adverse events	X	X	X	X	X	X	X	
Recording of concomitant medication	X	X	X	X	X	X	X	
Sunitinib dispensation record		X						
Dose record/sunitinib compliance		X	X	X	X			
TH-302 administration			X		X			
CT image tumour measurements ¹⁰	X	Every 8 weeks from D1C1 until progression and end of treatment visit.						
Collection and freezing of blood sample for marker tests ¹¹	X							
Shipment of tumour sample for marker tests ¹²	X							
Post-study survival ¹³								X

1. Patients will be required to sign two copies of the informed consent form. The patient must indicate his/her degree of consent with respect to the use of biological samples.
2. Medical record and demographic data: Includes but is not limited to: specific cancer history, date of diagnosis, type of primary tumour with histological diagnosis, previous surgical procedures and dates, and any other relevant medical history within the last 6 months.
3. Physical examination: weight, height, body surface area and vital signs: heart rate, blood pressure, body temperature.
4. Haematology and haemostasis: haematocrit, haemoglobin, platelet count, white blood cell count, red blood cell count, neutrophil count and lymphocyte count. Coagulation will include prothrombin time (PT), the international normalised ratio (INR) and activated partial thromboplastin time (APTT). This will be conducted at the baseline visit (≤ 7 days) and at each pre-treatment visit (± 3 days prior to day 8 and ± 1 day prior to day 22 of each cycle). It will also be conducted ± 1 day prior to day 15 to ensure a weekly follow-up of the patients.

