### Adverse Events

An adverse event is defined as any unwanted or unintended symptom, sign, disease or experience (including a clinically significant laboratory result of any grade according to the common terminology criteria for adverse events [CTCAE] of the National Cancer Institute, version 4.0) that emerges or worsens during the course of the study, whether related or not to the study drug.

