### 1.5.5. METHODS OF STATISTICAL ANALYSES

#### 1.5.5.1 Descriptive analysis

The descriptive analysis of patient characteristics will include demographic data, disease-specific data and prior treatments. Qualitative data will be described with absolute frequencies and corresponding percentages. Quantitative data will be studied using the mean  $\pm$  standard deviation, median, minimum and maximum values. The response percentages will be estimated using confidence intervals of 95%.

In the safety analysis, adverse events will be specified according to the maximum grade described at the discretion of the investigator and defined by NCI-CTCAE, version 4.0, including adverse events described from treatment initiation until 28 days following its completion.

The following safety analysis data will be presented:

- Temporary and permanent treatment discontinuations due to an adverse event.
- Deaths.
- Adverse Events (AEs) and Serious Adverse Events (SAEs).
- Hospitalisations.
- Use of concomitant medication and growth factors.

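### The SAP derives no CTCAE grades from the weekly laboratory values, so graded cytopenia and liver-test rates depend on investigator AE entry and may be understated

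*SAP*

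**What the plan says.** **Collection.** Protocol Annex 1 schedules haematology and clinical chemistry at screening, on days 1, 8, 15 and 22 of each cycle, and at end of treatment. The day 15 sample is there "to ensure a weekly follow-up of the patients".

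**Laboratory analysis.** SAP 2.8 states that "laboratory test results, physical examination findings and vital signs, and their changes from baseline will be summarized using descriptive statistics", followed by "Abnormal values will be flagged". SAP 1.5.5.1 describes quantitative data by the mean together with "standard deviation, median, minimum and maximum values".

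**Adverse events.** The definition in SAP 1.5.3 (and Protocol 10.2.2) takes in "a clinically significant laboratory result of any grade according to the common terminology criteria for adverse events". On grading, SAP 1.5.5.1 states that "adverse events will be specified according to the maximum grade described at the discretion of the investigator" and defined by CTCAE version 4.0.

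**Graded output.** SAP Table 34, headed Adverse events, is the only table in the SAP with columns by grade. It has rows for neutropenia, anaemia, thrombocytopenia, AST, ALT, GGT and alkaline phosphatase, among others. It has no row for bilirubin or creatinine.

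**The concern.** A grade 3 or 4 laboratory toxicity is defined by a number, and the trial measures that number every week. The natural safety summary is how many patients ever reached each grade. As planned, that count can come only from Table 34. An objective value seems to reach that table only after an investigator has judged it clinically significant, entered it as an event and graded it. In an open-label, single-arm study at 10 sites, reporting habits may differ between sites, and any omission lowers the rate.

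Safety is part of the study's main purpose (Protocol 1.12). Protocol 3.4 reports from the earlier sunitinib combination study that "Grade 3/4 neutropenia and thrombopenia was observed in 3 and 5 patients, respectively". The denominator for those counts is not clear from the text, so they give a signal but no rate. Low neutrophil and platelet counts also drive the dose changes in Protocol Table 2. A reader of the final report would therefore want a graded rate that does not vary with how each site completes its AE forms.

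**Working it through.** The documents give no cytopenia rate, safety sample size or precision target, so there is no figure to reproduce. The check follows a weekly value to the graded table, then shows the scale of a possible shortfall.

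**Step 1. The two routes for a laboratory value**

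- *Laboratory route (SAP 1.5.5.1, 1.5.5.4, 2.8).* The outputs are mean, SD, median, minimum, maximum, change from baseline, and a flag. None is a number of patients. The minimum shows the single lowest value, not how many patients were low. The flag has no threshold, no grade and no rule for reducing repeated weekly values to one result per patient.
- *AE route (SAP 1.5.3, 1.5.5.1, Table 34).* The value is judged clinically significant, entered as an event, given a maximum grade at the investigator's discretion, and counted. That Table 34 uses only this route is an inference from its title and from SAP 1.5.5.1. The SAP does not say so, but it names no other source.
- *Link between the routes.* There is no worst-grade table, no shift table and no reconciliation of AE entries with laboratory values. SAP Annex I, on database management and data cleaning, is still a placeholder.

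**Step 2. Scale, for illustration only**

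Inputs: N = 43 (SAP 1.5.4); true grade 3/4 rate p, assumed 20% or 30%; share c of those patients entered as AEs, assumed 100% to 50%. Neither p nor c is in the documents.

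Expected patients shown = N × p × c. Shortfall in percentage points = p × (1 − c).

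| p | c | N × p × c | Patients shown (about) | Rate shown | Shortfall |
|---|---|---|---|---|---|
| 20% | 100% | 43 × 0.20 × 1.0 = 8.6 | 9 | 20% | 0 |
| 20% | 90% | 43 × 0.20 × 0.9 = 7.74 | 8 | 18% | 2 points |
| 20% | 70% | 43 × 0.20 × 0.7 = 6.02 | 6 | 14% | 6 points |
| 20% | 50% | 43 × 0.20 × 0.5 = 4.3 | 4 | 10% | 10 points |
| 30% | 100% | 43 × 0.30 × 1.0 = 12.9 | 13 | 30% | 0 |
| 30% | 90% | 43 × 0.30 × 0.9 = 11.61 | 12 | 27% | 3 points |
| 30% | 70% | 43 × 0.30 × 0.7 = 9.03 | 9 | 21% | 9 points |
| 30% | 50% | 43 × 0.30 × 0.5 = 6.45 | 6 | 15% | 15 points |

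For comparison, the exact (Clopper-Pearson) 95% interval is 17.2% to 46.1% for 13/43 and 10.0% to 36.0% for 9/43. At 70% capture the shortfall is smaller than the sampling uncertainty. It goes in one direction, however, and the interval does not account for it.

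**The case against.** The strongest reply is that severe counts are the ones least likely to be missed. The AE definition is not limited to severe results ("including a clinically significant laboratory result of any grade"). Protocol Table 2 ties neutrophils below 1,000/µl or platelets below 75,000/µl to dose action, and Protocol 6.3 bases dose modifications on the most severe preceding toxicity. A count that triggers dose action is hard to call clinically insignificant. In addition, all AEs must be reported in full (Protocol 10.2.2), the monitor verifies CRF entries against laboratory reports (13.3), and reasons for reductions, delays and omissions are tabulated (SAP Tables 9 and 11).

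Much of this stands. A reader might infer that grade 3/4 cytopenia will be understated, and the documents do not support that. Under-recording is more plausible for milder abnormalities or those that prompt no action.

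The reply does not close the gap, for four reasons:

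- The duty to report all AEs applies only once a result has been judged to be an AE.
- Table 2 covers neutrophils and platelets only. Haemoglobin and transaminases appear among the reintroduction criteria in Protocol 6.3.2, so Table 2 gives no backstop for the anaemia and liver-test rows.
- Table 2's TH-302 columns are for days 8 and 22, while counts are also taken on days 1 and 15. Its sunitinib column calls for a one-level reduction, but level -1 in Protocol Table 1 lists the same sunitinib dose as the starting level. These passages and Protocol 6.3 must be reconciled before dose records can serve as a trace of low counts.
- Reasons for dose changes are not graded rates.

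A reader might also infer that the laboratory data are summarised only as mean changes. They are not: the values themselves are summarised, with median, minimum and maximum, and abnormal values are flagged. Nor can it be said that the rates would not be comparable with the earlier combination study, because the protocol does not say how those counts were obtained.

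**Conclusion.** The gap is real and moderate. The SAP plans no per-patient CTCAE grade from the scheduled laboratory values. The only graded cytopenia and liver-test rates appear to rest on investigator-entered events filtered by clinical significance. Those rates depend on site reporting and may be understated. The size cannot be derived from the documents: it is zero at full capture, and the table above shows how it grows if capture is incomplete.

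The conclusion rests on two readings: that Table 34 draws on AE entries, and that the weekly values are available for analysis, which the SAP presupposes by planning to summarise them. No decision rule depends on these rates, since continuation rests on responses (SAP 1.5.4). The point concerns the quality of the safety description and does not affect the primary conclusion.

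**What to change.** In SAP 2.8:

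1. Add a table of worst post-baseline CTCAE v4.0 grade and a baseline-to-worst-grade shift table for neutrophils, platelets, haemoglobin, AST, ALT, bilirubin and creatinine. Derive the grades by program from the recorded values, in all treated patients with a post-baseline value, and state that denominator.
2. Present these beside the AE-reported rows of Table 34, state the source of each, and list and reconcile discrepancies. The laboratory grades should not replace the AE rows, which may hold events found on unscheduled or outside tests.
3. Define the abnormal-value flags by CTCAE grade.

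The cost is SAP wording and a little standard programming on tests already scheduled. No visit, dose or eligibility rule changes. The reported rates may turn out less favourable.

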**Table 34. Adverse events**

Adverse Events	Grade 1 N (%)	Grade 2 N (%)	Grade 3 N (%)	Grade 4 N (%)	Total N (%)
Hematologic					
Neutropenia					
Anaemia					
Thrombocytopenia					
Metabolic/Laboratory					
GGT ( $\gamma$ -Glutamyl transpeptidase)					
Alkaline phosphatase					
Lipase					
AST, SGOT (serum glutamic oxaloacetic transaminase)					
ALT, SGPT (serum glutamic pyruvic transaminase)					
Gastrointestinal					
Nausea					
Diarrhoea					
Abdominal pain					
Constipation					
Vomiting					
Heartburn/dyspepsia					
Mucositis					
Others					
Hypertension					
Fatigue (asthenia)					
Dry mouth/salivary gland (xerostomia)					
Headache					
Anorexia					
Vaginal bleeding					
Fistula					
Hypothyroidism					
Subclinical Hypotiroidism					
Neuropathy					
Hepatic toxicity					

GGT: Gamma glutamil transpeptidase; AST: Aspartate aminotransferase; ALT: Alanine transaminase.

### **3. CONCLUSIONS**

## **4. ANEXES**

### **4.1. ANEX I: DATABASE MANAGEMENT**

In this section, the process of data base management and data cleaning will be described.

